Official title:

Blocking nocturnal blue light to treat insomnia: A pilot randomized controlled trial

NCT #:

NCT0268800

Date of Document:

July 26, 2018

Study Design:

The current proposal is for a randomized, placebo-controlled, crossover trial to test the effects of blocking nocturnal blue light exposure on sleep, sleep habits, and melatonin secretion in individuals with insomnia. This will be a combined ambulatory and laboratory investigation. The intervention will consist of wearing BB lenses which block 97% of blue light (Uvex amber lenses, Bandit wraparound glasses, Honeywell Safety, Smithfield, RI) or non-BB placebo lenses (Uvex clear lenses, Bandit wraparound glasses, Honeywell Safety, Smithfield, RI) for the 2 h preceding bedtime each night for 1 wk (**Fig. 2**). Intervention phases will be separated by a 4-wk washout period, to reduce carry-over effects and study premenopausal women at the same menstrual cycle phase. This will be followed by crossover to the alternate intervention phase. Each 1-wk intervention phase will conclude with an in-

[figure not shown]

Figure 2. The randomized, placebo-controlled, crossover design. AW: actiwatch; SSQ: subjective sleep quality.

patient laboratory visit to characterize the effects of the intervention on sleep and circadian physiology (**Fig. 3**). During the ambulatory portion, participants will be free-living and will expose themselves to their habitual light levels and choose their sleep timing. During the laboratory portion, an 8-h sleep episode will be scheduled based on participant's habitual sleep times during the week preceding entry. For standardization, and to demonstrate the beneficial effects of the BB lenses for preserving nocturnal melatonin secretion, participants will be uniformly exposed to an LED light source for 2 h preceding bedtime during the laboratory portion (**Fig. 3**).

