Individuals meeting inclusion criteria will be enrolled and randomized to receive either BB or placebo lenses in phase 1. Participants will be instructed to wear lenses each night, from 2 h before bedtime until lights out. Throughout the intervention, upon awakening participants will note their bedtime and waketime, and time of wearing lenses, on a sleep-log, and will complete a daily post-sleep questionnaire (**PSQ**). The PSQ entails quantitative estimates of SOL, total sleep time (**TST**), time awake during sleep episode, and number of awakenings, as well as ratings on a 7-point scale of overall evaluation of sleep (1: extremely bad, 7: extremely good), soundness of sleep (1: extremely light, 7: extremely sound), current feeling of sleepiness (1: not sleepy at all, 7: extremely sleepy), and current feeling of refreshed (1: not refreshed at all, 7: extremely refreshed) (42). This will allow us to confirm compliance with intervention and to collect data on ambulatory sleep quality and habits across the trial. During each intervention, participants will wear a wrist-mounted Actigraph GT3X+ to monitor TST, SOL, and sleep efficiency (**SE**). At the beginning of the intervention, participants will complete a brief computer-based adaptive neuropsychological battery (NIH Toolbox Cognition Battery; www.nihtoolbox.org) to assess their functioning in the domains of executive function, attention, episodic memory, language, processing speed, and working memory. This assessment will last about 30 minutes. CUMC research staff will interact with participants and setup the study.

Upon completing the 1-wk intervention, participants will be admitted to the Inpatient Unit at the Clinical Research Resource (CRR) of CUMC at ~18:00 for the lab testing period (Fig. 3). Upon admission, an in-dwelling forearm catheter will be inserted to allow continuous blood sampling which will not interrupt the sleep episode. Blood (3 ml/sample) will be collected continuously (1x/h) from 19:00-09:00 under “constant posture conditions”. Participants will remain in dim lights (<30 lux) and in a semi-recumbent position during wakefulness. The sleep episode will occur in total darkness in a fully recumbent position. In lieu of meals, small isocaloric servings of BOOST Plus Complete Nutritional Drink (Nestle) will be served each hour during wake episodes. Participants will be asked to stretch their legs each hour while in the bed during the lab portion, without getting out of bed.

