Within the first 2 hours of arrival in the lab, participants will complete the Pittsburgh Insomnia Rating Scale-65 (**PIRS65**), which quantifies insomnia symptom severity. They will also repeat the same brief (~30 min) neuropsychological battery (NIH Toolbox Cognition Battery) administered at the intervention. Each hour spent awake in the laboratory, participants will complete a 15-item visual analogue scale (**VAS**) to assess their levels of alertness, hunger, and appetite. CUMC research staff will interact with participants and conduct the study/collect data.

Beginning 2 hours before the sleep episode, participants will be exposed to bright light (500 lux) and will wear either BB or placebo lenses. The sleep episode will be scheduled based on their habitual sleep patterns during the previous week at home. They will have an 8-hour sleep opportunity in the lab. This will include a polysomnographic sleep recording. Upon awakening, participants will remain in bed in semi-recumbent position for the next 3 hours. Participants will complete the PSQ, and will resume the VAS scales, as well as have servings of BOOST Plus. At

9:00, blood sampling will end and the catheter will be removed. Participants will be discharged at 10:00. Blood samples will be analyzed for plasma content of melatonin (RIA, ALPCO, Salem, NH). After discharge, participants will begin a 4-week washout period. At the conclusion of this, they will cross over to the alternate lenses condition. They will be given the alternate lense type (BB or clear) and also the actigraph for the 7-day ambulatory tracking period. They will resume using the lenses 2-h before bedtime for 7 days, and completing the sleep-log and post-sleep questionnaires. After this, they will return to the lab for the second overnight visit. At the conclusion of the second overnight visit, they will have completed all experimental procedures.

Statistical Procedures:

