Two-way within subjects ANOVA for repeated measures (factors: condition x time) will be used to analyze continuous melatonin, VAS, and neuropsychological values obtained during the laboratory visits. Simple main effects tests will be used to analyze significant interactions. Paired-samples t-tests will be used to analyze single-value sleep parameters (subjective, actigraphic, and PSG), as well as sleep related questionnaires (PIRS65 and PSQ). Data will be tested for normality, and non-parametric equivalent tests will be used if data are deemed not normally distributed. Significance will be $p < 0.05$

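### The crossover analysis has no period or sequence term, so a visit-order effect costs precision and, if the sequences are uneven, shifts the lens estimate

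*Combined protocol and SAP*

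**What the plan says.** The Study Design section describes two one-week lens phases separated by a four-week washout, with lens order set by chance: "Individuals meeting inclusion criteria will be enrolled and randomized to receive either BB or placebo lenses in phase 1". It states no allocation ratio, blocking or target per sequence. The washout has two stated purposes: "to reduce carry-over effects and study premenopausal women at the same menstrual cycle phase".

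The Statistical Procedures section is the whole analysis plan. Single-value outcomes are handled thus: "Paired-samples t-tests will be used to analyze single-value sleep parameters (subjective, actigraphic, and PSG), as well as sleep related questionnaires (PIRS65 and PSQ". For the repeated measures: "Two-way within subjects ANOVA for repeated measures (factors: condition x time) will be used to analyze continuous melatonin, VAS, and neuropsychological values". If normality fails, "non-parametric equivalent tests will be used if data are deemed not normally distributed"; the tests are not named. Period, phase order and sequence appear nowhere. The time factor applies to values collected at the laboratory visits, so it reads most naturally as time within a phase, not as the order of the phases.

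**The concern.** A washout limits carry-over. It does not make a participant's second visit equivalent to the first. Two features of this design make a visit-order difference plausible:

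- **Laboratory night.** Each phase ends with one overnight stay with polysomnography and a blood-sampling line ("Upon admission, an in-dwelling forearm catheter will be inserted to allow continuous blood sampling"). No adaptation night is described, so everyone's first such night falls in period 1 and the next comes only at the end of period 2 ("After this, they will return to the lab for the second overnight visit").
- **Cognitive testing.** The same battery is given more than once ("They will also repeat the same brief (~30 min) neuropsychological battery (NIH Toolbox Cognition Battery) administered at the intervention"), so practice can raise later scores.

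If such an effect exists, the planned tests treat a systematic, estimable difference as random noise. That costs precision in a study described as a pilot. If chance or drop-out leaves the sequences uneven, part of the order effect is also reported as a lens effect, or hides one.

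**Working it through.** **Inputs.** From the documents: two periods, two conditions, randomized order, significance at p < 0.05. Sidedness is not stated; two-sided is assumed. Sample size, SD, effect size, drop-out and sequence split are not given, so there is no figure of the plan's own to reproduce. Assumed for illustration: N = 14 (also 10, 20 and 24), lens effect τ = 0.8, and period shift P = 0, 0.25, 0.5 or 1, all in units of s, the SD of the within-participant differences.

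**Algebra.** Let d be blue-blocking minus placebo within a participant, P the period 2 minus period 1 shift, n1 the number with blue-blocking lenses first, n2 the number with placebo first, and N = n1 + n2.

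- Expected d is τ − P with blue-blocking first and τ + P with placebo first.
- The paired mean therefore estimates τ + P(n2 − n1)/N.
- The variance used by the paired test is s² + P² × 4n1n2/[N(N − 1)] on average.
- The period-adjusted estimate is the average of the two sequence means of d. P cancels for any split. Its standard error is ½s√(1/n1 + 1/n2), on N − 2 degrees of freedom.

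**Equal sequences, 7:7.** The factor 4n1n2/[N(N − 1)] is 196/182 = 1.077. At P = 0.5 the SE inflation is √(1 + 0.25 × 1.077) = 1.127. Type I error and power are simulated (200,000 trials per setting):

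| P | SE inflation | Paired type I error | Paired power | Adjusted power |
|---|---|---|---|---|
| 0 | 1.000 | 0.05 | 0.79 | 0.78 |
| 0.25 | 1.033 | 0.044 | 0.77 | 0.78 |
| 0.5 | 1.127 | 0.029 | 0.71 | 0.78 |
| 1 | 1.441 | 0.006 | 0.47 | 0.79 |

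Other balanced sizes at P = 0.5, paired versus adjusted power: N = 10, 0.52 v 0.60; N = 20, 0.88 v 0.92; N = 24, 0.94 v 0.96.

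**Uneven sequences, N = 14, P = 0.5.**

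| Split | Shift in estimate (SD) | Paired type I error |
|---|---|---|
| 8:6 | 0.5 × 2/14 = 0.07 | 0.035 |
| 9:5 | 0.5 × 4/14 = 0.14 | 0.052 |
| 10:4 | 0.5 × 6/14 = 0.21 | 0.082 |

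At 10:4 with P = 1, type I error is 0.121. At 9:5 with P = 0.5, paired power is 0.85 if the shift runs with the lens effect and 0.53 if it runs against it; adjusted power is 0.75 either way.

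**How likely is an uneven split?** If allocation is simple 1:1 randomization (assumed), the exact binomial probability at N = 14 is 6946/16384 = 0.42 for 9:5 or worse and 2942/16384 = 0.18 for 10:4 or worse.

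**ANOVA.** With two conditions and complete data, the condition main-effect F is the square of the paired t on participant means, so it inherits the same loss. A simulation with 14 participants, 15 hourly samples and a 7:7 split gave power of 0.77, 0.71 and 0.48 at P = 0.25, 0.5 and 1, against 0.78–0.79 adjusted. The simple effects of condition are also affected. An additive visit shift cancels from the condition-by-time interaction, whose F was unchanged.

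**Non-parametric fallback.** If this means the paired signed-rank test, it has the same omission. Signed-rank versus rank-sum on period differences at 7:7 gives power of 0.78 v 0.71 (P = 0), 0.75 v 0.71 (0.25), 0.68 v 0.71 (0.5) and 0.42 v 0.71 (1).

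**The case against.** The planned test is valid on average. Over simple randomization the paired estimate is unbiased, with type I error of 0.049–0.052 for N = 10 to 24, and it is conservative when the sequences are equal. The shift is conditional on a split that nobody can yet state. All of this stands.

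The gain also depends on an unknown P. Averaged over simple randomization at N = 14, adjustment costs 4 points of power at P = 0 and 1.5 at P = 0.25; it gains 5.5 at P = 0.5 and 26 at P = 1. Break-even is near one third of an SD of the differences (paired v adjusted 0.755 v 0.751 at P = 0.30, 0.743 v 0.751 at P = 0.35). Nothing in the documents shows that P is that large. This stands too, but most of the cost comes from uneven sequences and largely disappears when they are near equal.

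The two named mechanisms reach only some outcomes. A first laboratory night cannot act on the PIRS65, completed soon after arrival, or on the period 1 home actigraphy and home PSQ. The cognitive battery goes to the ANOVA; if time there means start of phase versus laboratory visit, the lens effect lies in the interaction, from which an additive shift cancels. These limits are fair. They narrow the known routes to a period effect, but the algebra applies to an effect from any source.

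The rank-sum fallback is costlier at uneven splits: with P = 0, power is about 0.77 v 0.68 at 9:5 and 0.77 v 0.60 at 10:4. That is a real price, though it falls on a secondary analysis.

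**Conclusion.** The concern holds. Nothing in the plan handles a period effect in a two-period crossover. The main consequence is lost precision for single-value outcomes and condition main effects. Under the assumptions used (7:7, lens effect 0.8 SD), this is 1 point of power at P = 0.25, 7 at 0.5 and 32 at 1, relative to the adjusted analysis. The second is an estimate shifted by P times the sequence imbalance over N, for example 0.14 SD at 9:5 with P = 0.5. Type I error rises clearly only at marked imbalance such as 10:4. The omission and the direction of its effects do not depend on the assumed figures; their size does. The condition-by-time interaction is not affected by an additive shift. This should be fixed because the remedy is cheap; it is not a fatal flaw.

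**What to change.** 1. Analyse single-value outcomes with a mixed model: fixed condition, period and sequence, a random participant effect and a small-sample degrees-of-freedom method such as Kenward-Roger. For complete pairs this equals the two-sample comparison of period differences between sequences. Keep participants with only one completed phase in the model.
2. Add period and sequence to the melatonin, VAS and cognitive models.
3. Name the non-parametric fallback: the rank-sum test on period differences between sequences.
4. State how sequences are allocated and report the number in each. If allocation is still open, use blocks to keep the sequences near equal.
5. State that the period term does not correct differential carry-over.

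**Cost.** Analysis wording, one error degree of freedom and, if blocks are adopted, a new randomization list. With no period effect, adjusted power at N = 14 falls from 0.79 to 0.78 at 7:7, 0.75 at 9:5 and 0.70 at 10:4; at 5:5 it falls from 0.62 to 0.60. The rank-sum fallback costs about 6 points at 7:7 and roughly 9 to 17 points at 9:5 to 10:4, which is a further reason to block.
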